## Regimen U

Three patients will start at dose level U1. Dose escalation will proceed in each subsequent cohort according to the following scheme.

Table 4.1.4.1.1: 2 Treatment Schedule Regimen U

	Cohort	BIBW 2992
Regimen	Dose Cohort	mg/day
U	Cohort U1	20
U	Cohort U2b	30 *
U	Cohort U2	40

\*An intermediate dose cohort of BIBW 2992 at 30 mg may be explored if 40 mg is not tolerated (more than two patients with DLT).

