## CLINICAL TRIAL PROTOCOL SYNOPSIS

Name of company: Boehringer Ingelheim		Tabulated Trial Protocol
Name of finished product: Not Applicable		
Name of active ingredient: BIBW 2992		
Protocol date 3 April 2009	Trial number 1200.38	Planned trial period July 2009 – Jun 2015
Title of trial: Phase I, open label trial to explore safety of combining BIBW 2992 and Radiotherapy with or without Temozolomide in newly diagnosed GBM		
Co-ordinating Investigator: [REDACTED] Tel: [REDACTED] /Fax: [REDACTED]		
Trial sites: Multicenter Trial		
Clinical phase: I		
Objectives: Regimen U: Determination of the maximum tolerated dose (MTD) of BIBW 2992 administered in combination with radiotherapy in patients with newly diagnosed malignant gliomas (WHO grade IV) with an unmethylated MGMT-promoter. Regimen M: Determination of the maximum tolerated dose (MTD) of BIBW 2992 in combination with TMZ and radiotherapy in patients with newly diagnosed malignant gliomas (WHO grade IV) with a methylated or an unmethylated MGMT-promoter.		
Methodology: Open-label, stratified (Phase I) study		
No. of patients: total: Up to 60 patients each treatment: Up to 30 patients in each regimen (2-regimen study);		
Diagnosis and main criteria for inclusion: - Newly diagnosed malignant glioma (WHO Grade IV). - Tumour material available for MGMT testing unless MGMT test results already available.		
Test products: BIBW 2992 (film-coated tablets)		
dose: During RT (6 weeks): Regimen U and M: Dose escalation of daily BIBW2992 (20,40 mg) with one de-escalation step (30 mg) in case 40mg is not tolerated. After RT: Regimen U: 40 mg/day BIBW 2992 until either progressive disease or undue adverse reaction, whichever occurs first. Regimen M: 40 mg/day during concomitant TMZ/ BIBW 2992 treatment period followed by 40 mg/day BIBW 2992 monotherapy until either progressive disease or undue adverse reaction, whichever occurs first.		

Name of company: Boehringer Ingelheim		Tabulated Trial Protocol	
Name of finished product: Not Applicable			
Name of active ingredient: BIBW 2992			
Protocol date 3 April 2009	Trial number 1200.38	Planned trial period July 2009 – Jun 2015	
mode of admin. : Oral			

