##### **4.1.4.1.1 Dose escalation scheme for BIBW**

Initially, 3 evaluable patients will be treated per dose level. As soon as one patient experiences a DLT (see section 5.2.3), 3 new patients will be treated at that dose level, to treat a minimum of 6 evaluable patients. If no other patients experience DLT the dose will be escalated to the next level and 3 further patients treated. If two or more of six patients

experience DLT, three additional patients will be treated at one dose tier below unless six have already been treated at that dose tier.

The MTD (see section 5.2.4) is the highest dose at which no more than one of 6 patients experiences DLT. Once the MTD is determined, patient enrolment at higher dose tiers will be suspended.

The MTD cohort in each Regimen may be expanded to include up to 12 patients.

Intra-patient dose escalation will not be permitted.

The first three patients at each dose level will be treated and observed for at least 6 weeks (42 days) during RT before the next cohort of new patients are treated at the next higher dose level (Table 4.1.4.1.1: 2 and 4.1.4.1.1: 3).

Table 4.1.4.1.1: 1 Rules for dose escalation for regimen M and U

Number of Patients with DLT at a Given Dose Level	Escalation Decision Rule
0 out of 3	Enter 3 patients at the next dose level.
1 out of 3	Enter at least 3 more patients at this dose level. - If 0 of these 3 patients experience DLT, proceed to the next dose level. - If 1 or more of this group suffer DLT, then dose escalation is stopped. Three (3) additional patients will be entered at the next lower dose level if only 3 patients were treated previously at that dose.
$\geq 2$ out of 3	Dose escalation will be stopped. Three (3) additional patients will be entered at the next lower dose level if only 3 patients were treated previously at that dose.

The decision regarding dose escalation steps will only be made after agreement with the sponsor's Trial Clinical Monitor (TCM).

Dose escalation and entry of patients into the next dose cohort will begin only after accrual of the required minimum number of patients has been achieved and all patients in the cohort are considered following completion of 6 weeks BIBW2992 treatment ((42 days ) during RT). Patients who are not treated until the end of these 6 weeks for any reasons other than DLT will be replaced (section 6.3.1).

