### 5.2.4 Maximum Tolerated Dose (MTD)

7. The MTD is defined as:
8. The dose of BIBW 2992 when given concomitantly with TMZ and RT (Regimen M) or BIBW 2992 when given concomitantly with radiotherapy (Regimen U) which is one dose tier below that dose at which two or more out of six patients experienced drug-related DLTs during the 6 weeks (42-day) RT treatment period. DLT experienced after the start of the maintenance treatment period will be examined separately. At the MTD, no more than one patient out of six patients may experience DLT, i.e., MTD is defined as the

highest dose studied for which the incidence of DLT is no more than 17% (i.e. 1/6 patients).

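### The 30 mg footnotes call 40 mg not tolerated only at three or more DLTs, while every other rule rejects a dose at two, so exactly two DLTs leaves the 30 mg step without a stated trigger

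*Protocol*

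**What the plan says.** The planned doses are 20 mg and 40 mg, with 30 mg as an optional intermediate. The footnotes to Table 4.1.4.1.1: 2 (Regimen U) and Table 4.1.4.1.1: 3 (Regimen M) are the only places that attach a DLT count to opening 30 mg. Each says the cohort "may be explored if 40 mg is not tolerated (more than two patients with DLT"). No denominator is given.

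The other rules use a lower count:

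- **Section 4.1.4.1.1, prose.** At two or more of six, "three additional patients will be treated at one dose tier below unless six have already been treated at that dose tier".
- **Table 4.1.4.1.1: 1.** Escalation stops at two or more of three, or at one of three followed by at least one of the next three. Then three "additional patients will be entered at the next lower dose level if only 3 patients were treated previously at that dose".
- **Section 5.2.4.** The MTD is the dose "which is one dose tier below that dose at which two or more out of six patients experienced drug-related DLTs". It is also described as the "highest dose studied for which the incidence of DLT is no more than 17"%, given as 1/6.
- **Synopsis.** Escalation is planned "with one de-escalation step (30 mg) in case 40mg is not tolerated", with no count.

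Two further provisions matter. On expansion: "The MTD cohort in each Regimen may be expanded to include up to 12 patients". On oversight: "The decision regarding dose escalation steps will only be made after agreement with the" sponsor's Trial Clinical Monitor. SAP Section 7.4 takes the MTD from protocol Section 5.2.4 and does not restate the 30 mg trigger.

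**The concern.** The MTD is the primary endpoint in each regimen, and Section 5.2.4 confines it to doses actually studied. Whether 30 mg is opened therefore decides whether it can be the answer.

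After exactly two DLTs at 40 mg, the passages support different next steps. The footnote read with Table 4.1.4.1.1: 1 points to 20 mg: the 30 mg count is not reached, and the table's condition that three patients have already been treated describes 20 mg, not a cohort nobody has entered. The prose read with the synopsis points to 30 mg. The first route can end with an MTD of 20 mg and 30 mg untested. Because the two regimens recruit in parallel, the same result could also be handled differently in each.

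**Working it through.** **1. The plan's own figures.** 1/6 = 16.7%, which rounds to the stated 17%. Section 7.6: 2 × (12 + 6 + 6) = 48, as stated.

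**2. The thresholds at exactly two DLTs.**

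| 40 mg result | Incidence | Other rules | Footnote trigger (at least 3) |
|---|---|---|---|
| 2 of 3 | 66.7% | rejected (escalation table) | not met |
| 2 of 6 | 33.3% | rejected (prose, table, Section 5.2.4) | not met |
| 2 of 12 | 16.7% | within 17% | not met |
| 3 of 12 | 25.0% | above 17% | met |

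The conflict sits in the first two rows. The footnote count agrees with the 17% ceiling in a cohort expanded to 12, but the footnotes belong to the escalation tables, where cohorts are normally three to six, and do not mention expansion.

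**3. How often the thresholds conflict.** The documents give no true DLT rate for 40 mg with radiotherapy, so a range of p is assumed. Low rates are included because Section 1.2.1 reports 40 mg with temozolomide, without radiotherapy, as well tolerated. Everything is conditional on reaching 40 mg, and 0 of 3 counts as a pass.

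Let Pk = C(3,k) p^k (1 − p)^(3−k).

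- 40 mg fails: 1 − (P0 + P1·P0).
- Fails with exactly two, table rule (stop at two of three): P2 + P1·P1.
- Fails with exactly two, prose rule (any cohort with a DLT filled to six): P1·P1 + P2·P0.

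Example at p = 0.30: P0 = 0.343, P1 = 0.441, P2 = 0.189.

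- Fail: 1 − (0.343 + 0.441 × 0.343) = 0.506.
- Table rule: 0.189 + 0.441² = 0.383.
- Prose rule: 0.441² + 0.189 × 0.343 = 0.259.

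| Assumed p | 40 mg fails | Exactly two, table rule | Exactly two, prose rule |
|---|---|---|---|
| 0.10 | 0.094 | 0.086 | 0.079 |
| 0.167 | 0.220 | 0.190 | 0.161 |
| 0.20 | 0.291 | 0.243 | 0.197 |
| 0.30 | 0.506 | 0.383 | 0.259 |
| 0.40 | 0.691 | 0.475 | 0.249 |
| 0.50 | 0.828 | 0.516 | 0.188 |

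Under the table rule, exactly two DLTs accounts for 92% of failures at p = 0.10 and 62% at p = 0.50.

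**4. Sensitivity to the 0 of 3 convention.** 40 mg is the top dose and Section 5.2.4 refers to six patients, so a 0 of 3 cohort might also be filled to six. That adds P0·P2 to the table-rule figure. At p = 0.30 this is 0.343 × 0.189 = 0.065, taking 0.383 to 0.448. The convention used therefore understates the table-rule figures.

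**The case against.** The strongest reply is that the MTD rule itself is clear. The SAP takes the MTD from Section 5.2.4, which sets it one tier below a dose with two or more of six. The dose tables list 30 mg directly below 40 mg, the prose sends patients one tier down, and the synopsis names 30 mg as the de-escalation step. The footnote is permissive and does not make its count a necessary condition. Dose escalation steps also need the sponsor's agreement. All of this stands. A reader might infer that the plan forbids 30 mg after two DLTs; the documents do not support that.

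Second, the table's condition about three patients already treated fits an unopened 30 mg cohort just as badly after three DLTs as after two. That also stands: it is a separate wording fault, not caused by the footnote count.

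Third, the percentages rest on assumed rates and do not measure harm. This stands too. A reader might take 9% to 52% as the chance of skipping 30 mg or of reporting a wrong MTD. Neither follows, because the prose, Section 5.2.4 and the synopsis leave 30 mg open.

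Fourth, the count of more than two could have been meant for a cohort expanded to 12. The arithmetic fits, but nothing in the footnotes says so.

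What remains is that a numeric threshold feeding the primary endpoint disagrees with the definition it should serve, and no passage reconciles them. Discretion can work around that, but it does not make the rule clear.

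**Conclusion.** The inconsistency holds in both regimens and does not depend on any assumed DLT rate. With exactly two DLTs in three to six patients, 40 mg is rejected and the only numeric trigger for 30 mg is not met. A literal reading could then leave 20 mg as the MTD with 30 mg untested.

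The consequence is limited. 30 mg remains available under other passages, and the likely intent is two or more. A reader might infer an overdosing risk, but the direction is the opposite: the result could be a dose one tier too low.

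The conflict would arise often enough to matter. Given that 40 mg is reached, the chance per regimen is 9% to 52% under the table rule and 8% to 26% under the prose rule, for assumed true rates of 10% to 50% and with 0 of 3 counted as a pass. The frequency with which 30 mg would actually be skipped is lower, and the documents do not allow it to be estimated. This is a wording fault that should be corrected, not a flaw in the design.

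**What to change.** Replace the parenthesis in both footnotes with: *40 mg exceeds the MTD per Section 5.2.4: two or more patients with DLT among the first six or fewer, or a DLT incidence above 17% in any larger or expanded cohort.*

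The second clause is needed because simpler wordings misfire:

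- A bare count of two or more would reject 2 of 12 (16.7%), which meets the ceiling.
- Two or more of up to six would miss 3 of 12 (25%), which the current footnote does catch.
- It would also miss 2 of 7 (28.6%), possible because Section 4.1.2 lets simultaneous entries overfill a cohort.

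Separately, word Table 4.1.4.1.1: 1 so that after 40 mg fails, the 30 mg cohort may be opened even if nobody has yet been treated there. 30 mg can stay optional.

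The cost is wording in two footnotes and one table. Planned enrolment does not rise, since the 48 patients in Section 7.6 already allow three cohorts per regimen (12 + 6 + 6 = 24). A run that opens 30 mg does use more patients than one that skips it: up to 24 per regimen, against up to 18 (12 + 6) if 30 mg is skipped and 20 mg is expanded to 12.

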## Regimen M

Three patients will start at dose level M1. Dose escalation will proceed in each subsequent cohort according to the following scheme.

Table 4.1.4.1.1: 3 Treatment Schedule

	Cohort	TMZ Dose	BIBW 2992
Regimen	Dose Cohort	mg/m  x 42days	mg/day
M	Cohort M1	75	20
M	Cohort M2b	75	30 *
M	Cohort M2	75	40

\* An intermediate dose cohort of BIBW 2992 at 30 mg may be explored if 40 mg is not tolerated (more than two patients with DLT).

### 4.1.4.1.2 Dose reduction scheme for BIBW: Regimen U and M

If a patient develops side effect that meets criteria for DLT (for definition refer to Section 5.2.3) regardless of treatment cycle, treatment with BIBW 2992 must be paused. If all drug-related adverse events recover to CTCAE Grade 1 or baseline (whichever is higher) within 14 days of stopping treatment with BIBW 2992, treatment may be resumed with dose reductions according to Table 4.1.4.1.2: 1. Otherwise, the patient will be taken off study. Exceptions to this are patients who derive obvious clinical benefit according to the investigator's judgment. These patients could be considered in agreement with BI's Trial Clinical Monitor (TCM) for further treatment.

If a patient need to dose reduced BIBW 2992 during RT, the dose of BIBW 2992 during the maintenance period will need to be discussed and decided on a case to case base between BI Trial Clinical Monitor and the investigator at site (keep BIBW2992 reduced daily dose or change as planned for 40mg BIBW2992 daily)

Table 4.1.4.1.2: 1 Dose reduction scheme for Regimen M and U

Treatment prior to treatment pause and dose reduction BIBW (mg)	Dose reduction		
	1 st DLT BIBW (mg)	2 nd DLT BIBW (mg)	3 rd DLT
20	Off-study		
30	20	Off-study	
40	30	20	Off-study

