#### b) Non-hematologic adverse reaction:

1. CTCAEv3 Grade  $\geq 3$  nausea or vomiting is occurring despite appropriate use of standard anti-emetics for at least three days.
2. CTCAEv3 Grade  $\geq 3$  diarrhoea despite appropriate use of standard anti-diarrheal therapy for at least three days.
3. CTCAEv3 Grade  $\geq 3$  rash despite standard medical management as outlined in Section 4.2.3 and lasting  $>7$  days.
4. CTCAEv3 Grade  $\geq 2$  cardiac left ventricular function.
5. CTCAEv3 Grade  $\geq 2$  worsening of renal function as measured by serum creatinine, newly developed proteinuria, or newly developed decrease in glomerular filtration rate.
6. All other non-hematological toxicities of CTCAEv3 Grade  $\geq 3$

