### 6.3 REMOVAL OF PATIENTS FROM THERAPY OR ASSESSMENT

A patient can be withdrawn from study treatment after discussion between the BI Clinical Monitor and the investigator.

A patient will be withdrawn from the study treatment:

- the patient is no longer able to participate in the study (e.g., AE, surgery, concomitant diagnoses, concomitant therapies or administrative reasons); in such a case the investigator's reason for a patient's removal must be recorded on the EOT page of the eCRF.
- significant deviation from the protocol or eligibility criteria; such patients will be considered protocol violations and removed from study.
- non-compliance with study or follow-up procedures.
- Patient not recovered from any DLT 14 days after the last administration of the study drugs. Recovery is defined as return to baseline level or CTCAE Grade 1, whichever is higher. Exception to this in patients who derive obvious clinical benefit according to the investigator's judgement could be considered upon discussion with BI's Clinical Monitor Local (CML). The dose reduction scheme provided in Table 4.1.4.1.2: 1 should be followed in this case.
- repeated episodes of drug related adverse reaction despite dose reductions
- documented progressive disease as defined in Section 5.1.3
- Cardiac left ventricular systolic dysfunction CTCAE Grade  $\geq 2$  at any time during the previous cycle or  $>20\%$  decline in the resting ejection fraction from baseline.

A patient will be withdrawn from the study if:

- patient withdrawal of consent and election to discontinue participation in the trial. Dates of patient withdrawal will be documented and the reason(s) for withdrawal recorded and discussed in the final study report.
- termination of the study by the sponsor

As soon as a patient is withdrawn from the trial, the next scheduled visit and the EOT have to be performed if feasible (not in case patient has withdrawn consent). Every effort should be made to follow-up patients in case an adverse event is still ongoing at the time of withdrawal.

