C3.2	TMZ non-compliance during concomitant treatment period (Regimen M only)	For patients in Regimen M only: Total number of doses of TMZ missed for reasons other than AE is more than 8 during concomitant treatment period.
C4	Trial specific PVs related to trial medication	
C4.1	Dose reduction scheme for afatinib not followed	Regardless of treatment period, incidence of DLT without subsequent adherence to the dose reduction scheme described in Section 4.1.4.1.2 of the CTP.
C4.2	TMZ treatment continued but re-treatment criteria not met (Regimen M only)	For patients in Regimen M only: Following the concomitant treatment period, TMZ not terminated despite re-treatment criteria described in Section 4.1.4.2 of CTP not met.
D	Concomitant medication	
D1	Prohibited concomitant medication	
D1.1	Prohibited medication use before the start of study treatment period	Inclusion criteria IN6 is not met. or At least one of exclusion criteria EX1-EX5 is met. or Prohibited concomitant therapy use before start of study treatment (defined in Sections 3.3.1 and 3.3.2 of the CTP).
D1.2	Prohibited medication use during study treatment period	Prohibited concomitant therapy use during study treatment (defined in Section 4.2.2 of the CTP).
D2	Mandatory medication not taken	
D2.1	Incorrect dose of radiotherapy administered during the concomitant treatment period	Radiotherapy total dose not equal to 60 Gy.
D2.2	Pneumocystis pneumonia prophylaxis not taken during concomitant treatment period (Regimen M only)	For patients in Regimen M only: Concomitant therapy use during concomitant treatment period does not include appropriate prophylaxis.
G	Trial specific protocol violations	
G1	Non-adherence to safety withdrawal criteria	Trial medication continued despite withdrawal criteria in Section 6.3 of the CTP met.
G2	Other protocol violations affecting patient rights or safety	Any other protocol violation that affects the rights or safety of trial patients.

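### After a DLT, Protocol 4.1.4.1.2 and 6.3 disagree on whether a recovered left ventricular event may be re-treated and, in Regimen M, on when the 14-day recovery period starts

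*Protocol*

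**What the plan says.** Protocol 5.2.3 (non-hematologic list, item 4) makes Grade 2 or higher "cardiac left ventricular function" a DLT, provided the event is considered related to BIBW 2992.

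Protocol 4.1.4.1.2 has a general trigger: "If a patient develops side effect that meets criteria for DLT (for definition refer to Section 5.2.3) regardless of treatment cycle". BIBW 2992 is then paused. If all drug-related adverse events return to Grade 1 or baseline "within 14 days of stopping treatment with BIBW 2992, treatment may be resumed with dose reductions", following Table 4.1.4.1.2: 1. If they do not, "Otherwise, the patient will be taken off study", apart from a clinical-benefit exception agreed with the Trial Clinical Monitor.

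Protocol 6.3 opens its list with "A patient will be withdrawn from the study treatment". Two entries matter here. One is "Patient not recovered from any DLT 14 days after the last administration of the study drugs", which has a clinical-benefit exception and refers back to the dose-reduction table. The other is "Cardiac left ventricular systolic dysfunction CTCAE Grade" 2 or higher at any time in the previous cycle, or a fall of more than 20% in resting ejection fraction from baseline. It has neither a recovery clause nor an exception.

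SAP Table 6.2: 1 lists two relevant important protocol violations. C4.1 covers a DLT after which the 4.1.4.1.2 scheme is not followed. G1 reads "Trial medication continued despite withdrawal criteria in Section 6.3 of the CTP met".

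**The concern.** Two sections govern the same patient after a DLT, and neither says which prevails.

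(a) A drug-related left ventricular DLT that recovers in time may be re-treated at a lower dose under 4.1.4.1.2, while 6.3 calls for withdrawal. A site that uses the permission satisfies C4.1 and is coded under G1 for the same act.

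(b) The 14-day limit starts from BIBW 2992 alone in one section and from the study drugs, plural, in the other. In Regimen M these can be different days.

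At stake is whether and when a patient is re-exposed or taken off treatment. Exposure and the description of protocol violations would then depend partly on which section a site had read.

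**Working it through.** The protocol gives no figure to reproduce. The check is a comparison of wording plus one line of arithmetic.

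**Part (a): the two rules side by side**

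| | 4.1.4.1.2 | 6.3, left ventricular entry |
|---|---|---|
| Trigger | Any DLT, any cycle (for this event: Grade 2 or higher, related to BIBW 2992) | Grade 2 or higher in the previous cycle, or a fall in ejection fraction of more than 20%; no relatedness condition |
| If recovered in 14 days | May resume at a reduced dose | Withdrawn from study treatment |
| Exception | Clinical benefit, if not recovered | None |

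The triggers overlap but are not identical. The overlap is a drug-related Grade 2 or higher event in a period that counts as the previous cycle.

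Who can meet the conflict follows from Table 4.1.4.1.2: 1:

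- From 20 mg: the first DLT is off study, so no conflict.
- From 30 mg: the first DLT allows a lower dose; the second is off study.
- From 40 mg: the first and second DLTs allow a lower dose; the third is off study.

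So 3 of the 6 filled cells (0 + 1 + 2 of 1 + 2 + 3) leave a step. The event must also recover within 14 days; otherwise both sections lead off treatment, leaving aside the case-by-case exception. Planned maintenance is 40 mg in both regimens (4.1.3), so patients from any cohort could later be at a dose with a step left.

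Two further limits apply. The visit schedule numbers cycles only after radiotherapy, so the reach of the 6.3 entry during the 42-day phase is unclear. Echo or MUGA is scheduled only at screening and end of treatment (6.2), so an event during treatment would come to light only through an unscheduled assessment. The documents give no basis for an event frequency.

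**Part (b): the two limits**

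Let d be the day of the last BIBW 2992 dose before the pause and t the day of the last TMZ dose, with t no earlier than d.

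- Limit under 4.1.4.1.2: d + 14.
- Limit under 6.3, taking the study drugs in Regimen M as both drugs: t + 14.
- Gap: (t + 14) − (d + 14) = t − d.

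Section 5.2.3 supports that reading, since its hematologic list refers to both study drugs. The drugs can stop on different days because 4.1.4.1.2 pauses BIBW 2992 only, while TMZ interruption follows its own product information (4.1.4.2).

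The largest gap in the concomitant phase has t = 42, the last planned TMZ day, which gives 42 − d:

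| d | Limit, 4.1.4.1.2 | Limit, 6.3 | Gap (days) |
|---|---|---|---|
| 7 | Day 21 | Day 56 | 35 |
| 14 | Day 28 | Day 56 | 28 |
| 21 | Day 35 | Day 56 | 21 |
| 28 | Day 42 | Day 56 | 14 |
| any, both drugs stopped together | d + 14 | d + 14 | 0 |
| any, Regimen U | d + 14 | d + 14 | 0 |

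**Effect on the primary endpoint**

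The event is a DLT under either section. Protocol 5.2.4 and SAP 5.1 count it by onset in the 42-day period, not by what happens afterwards, and 6.3.1 does not replace patients who stop because of a DLT.

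**The case against.** The best defence is that no site is forced into a breach. Section 4.1.4.1.2 only permits resumption, whereas 6.3 is mandatory and more specific, so a site can pause and then withdraw the patient without offending either section. For the 14 days, acting at the earlier limit satisfies both, because 6.3 sets a condition for removal and does not require keeping a patient until then. The sections also share the 14 days, the recovery target and a clinical-benefit exception, and 6.3 refers to the dose-reduction table.

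Much of this stands, and it limits the point. A reader might infer that any site following 4.1.4.1.2 commits a violation; only a site that chooses to resume does. A reader might infer that every left ventricular DLT is affected; the dose table and the recovery condition rule that out. A reader might take Day 56 as typical; it needs uninterrupted TMZ to Day 42 despite an unrecovered DLT, and for persistent diarrhoea, nausea, vomiting and rash Section 4.2.3 provides for pausing either or both drugs.

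What does not stand is the claim that the permission yields to the mandate. Neither section says so, and neither cross-refers on left ventricular events. A permission whose use is coded as an important protocol violation is a contradiction, even if a careful site can avoid it.

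**Conclusion.** The two sections conflict as written and should be reconciled.

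Part (a) is limited to drug-related left ventricular DLTs with a dose step remaining and recovery within 14 days. Its reach during radiotherapy is unclear because the previous cycle is not defined there.

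Part (b) is limited to Regimen M with TMZ continuing after BIBW 2992 is paused. The gap is at worst 42 − d days in the concomitant phase, on the assumptions that the study drugs means both drugs and that TMZ runs to Day 42. Otherwise it can be as small as zero, and in Regimen U it is always zero.

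The stronger inference, that the MTD is put in doubt, is not supported: the DLT count is the same under either rule. Nor does G1 coding remove anyone from analysis. SAP 6.2 defines no per protocol set and only describes violations, and SAP 6.3 uses the treated set throughout. The effect is on patient handling, exposure and violation classification.

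**What to change.** Amend Protocol 4.1.4.1.2 and 6.3 together:

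- Cross-refer the two sections so that a single rule applies to left ventricular DLTs.
- Say how the previous cycle in 6.3 is to be read during the radiotherapy phase.
- Define one start for the 14-day period and use it in both sections, naming the drug or drugs for Regimen M.
- In the same edit, align three smaller differences: recovery of all drug-related events (4.1.4.1.2) or of the DLT (6.3); off study or off study treatment; and which sponsor monitor is consulted on the exception.

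Which clinical rule applies is for the clinical team; this review takes no position. SAP C4.1 and G1 already point to these two sections, so they follow the reconciled text without a separate edit. The cost is amendment wording in two sections, with no extra visits or data.
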